## 7.8 Subgroups of Interest

Primary efficacy endpoint, secondary efficacy endpoints and selected safety variables (treatment emergent adverse events) will be summarized by the treatment group for the subgroups defined on the basis of the categorized variables listed in [Table 12].

**Table 12 Subgroups of Interest**

Item	Classification	Endpoints to be assessed
Sex	1: Male 2: Female	Primary efficacy endpoint, Secondary efficacy endpoints, TEAEs
Age (years) [Informed Consent]	1: < 70 2: >= 70	Primary efficacy endpoint, Secondary efficacy endpoints, TEAEs
Left Ventricular Ejection Fraction (%)	1: < 40 2: >= 40	Primary efficacy endpoint, Secondary efficacy endpoints
AKIRisk Score ((ng/mL)  /1000) [Postsurgery]	1: > 0.3 to <= 0.7 2: > 0.7	Primary efficacy endpoint, Secondary efficacy endpoints
Diabetes Mellitus	1: No 2: Yes	Primary efficacy endpoint, Secondary efficacy endpoints
Peripheral Arterial Disease	0: No 1: Yes	Primary efficacy endpoint, Secondary efficacy endpoints
Use of Intravenous Radio-contrast	0: No 1: Yes	Primary efficacy endpoint, Secondary efficacy endpoints
Surgery Type 	1: Lower Risk Surgery 2: Higher Risk Surgery	Primary efficacy endpoint, Secondary efficacy endpoints
Duration of CPB (hours)	1: < Median 2: >= Median	Primary efficacy endpoint, Secondary efficacy endpoints
Duration of Aortic Cross-Clamp (hours)	1: < 0.5 2: >= 0.5 to < 1.0 3: >= 1.0	Primary efficacy endpoint, Secondary efficacy endpoints
eGFR based on Serum Creatinine (mL/min/1.73 m  ) [Baseline]	1: < 45 2: >= 45	Primary efficacy endpoint, Secondary efficacy endpoints, TEAEs
	1: < 60 2: >= 60	Primary efficacy endpoint, Secondary efficacy endpoints, TEAEs
Protocol Version Number at Enrollment	1: Before Version 2.0 2: Version 2.0 or Later	Primary efficacy endpoint, Secondary efficacy endpoints
Time of First Study Drug Taken	1: Within T0 + 8 hours 2: After T0 + 8 hours	Primary efficacy endpoint, Secondary efficacy endpoints
Protocol Version Number at Enrollment and Time of First Study Drug Taken	1: [Before Version 2.0] and [Within T0 + 8 hours] 2: [Before Version 2.0] and [After T0 + 8 hours] 3: [Version 2.0 or Later] and [Within T0 + 8 hours] 4: [Version 2.0 or Later] and [After T0 + 8 hours]	Primary efficacy endpoint, Secondary efficacy endpoints

TEAE: treatment-emergent adverse event; CPB: cardiopulmonary bypass pump; eGFR: estimated glomerular filtration rate

1: If the procedure of surgery is only one of CABG, Valve Surgery [Aortic], Valve Surgery [Mitral] or Valve Surgery [Tricuspid] and not Thoracic Aortic Surgery then Surgery type is “Lower Risk Surgery”; otherwise “Higher Risk Surgery”.

For more details refer to [Section [7.4.3](#) and [7.5.1](#)].

## 7.9 Other Analyses

### 7.9.1 Analysis for Observational Cohort

[Analysis population: PFAS, Analysis group: Weighted Total (PFAS)]

Potential risk factors (demographics, subject characteristics, biomarkers) for development of AKI and MAKE (AKI-SCr72h, AKI-SCr7d, MAKE30, and MAKE90) will be explored. Population standardization is used in this analysis. Weighted Total (PFAS) is the set of NC negative group and NC positive group weighted by (the number of subjects assigned to Placebo group + the number of subjects assigned to ASP1128 group)/ (the number of subjects in Placebo group). The estimate of the unadjusted risk ratio, 2-sided 90% confidence interval, true positive rate, and true negative rate for AKI and MAKE (AKI-SCr72h, AKI-SCr7d, MAKE30, and MAKE90) proportion will be calculated by risk factors listed in [\[Table 13\]](#). In Analysis for Observational Cohort, subjects whose status of AKI and MAKE is unknown due to, say, the missing data of SCr will not be counted as AKI/MAKE event. This treatment for missing data is different from it for primary and secondary endpoints.

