### Observational Cohort

If at randomization NC is negative (AKIRisk score is  $\leq 0.3$  (ng/mL) $^2/1000$  at all assessments between 2 and 22 hours after T0), the subject cannot be randomized. These subjects will be included in the observational cohort. The observational cohort will enroll a maximum of 440 subjects. The aim of following up the subjects in the observational cohort is to further evaluate the AKIRisk score, as well as other risk factors (including clinical characteristics and biomarkers) for AKI and MAKE. Clinical endpoints will be investigated in the subgroups defined by AKIRisk score at randomization and other baseline risk factors, in the population of the NC positive subjects, who are randomized to the active or the placebo group, and the NC negative subjects, who are in the observational cohort. The subjects in this cohort can be discharged at the discretion of the investigator and will be followed up after surgery for assessment of AKI up to 7 days (acute kidney injury based on serum creatinine KDIGO criteria [AKI-SCr] using SCr values from local laboratory testing and 24-hour UO to assess stage 3 AKI-UO) and for assessment of MAKE event at day 30 and day 90. Hospital and ICU stay will also be recorded. AEs and medication use will be recorded until 24 hours after T0. Urine samples will be collected for NephroCheck® (NC) and biomarker assessments. If available, local laboratory test results and 24-hour UO data will be collected from medical records. No additional blood samples will be taken for study purposes after visit 2. See Schedule of Assessments [[Table 2](#)].

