### **4.5 Assignment and Allocation**

Subjects who have a NC AKIRisk score of  $> 0.3 \text{ (ng/ml)}^2/1000$  will be randomized in a 1:1 ratio to a treatment arm according to the randomization schedules through IRT. There will be a cap on the proportion of subjects randomized with a eGFR  $< 45 \text{ mL/min per } 1.73 \text{ m}^2$  (assessed at visit 1 as per CKD-EPI equation) of 20% of total randomized. Randomization will also be stratified for eGFR  $< 45$  and  $\geq 45 \text{ mL/min per } 1.73 \text{ m}^2$  to allocate subjects equally between study groups within each stratification. The site personal will dispense the treatment according to the IRT system's assignment. Specific procedures for randomization through the IRT are contained in the study procedures manual.

Subjects with NC AKIRisk score of  $0.3 \text{ (ng/mL)}^2/1000$  or less will be enrolled in the observational cohort. The observational cohort will enroll a maximum of 440 subjects.

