### I. The purpose of this amendment is:

| Substantial Changes                              |   |
|---|---|
| 1. Changes in Enrollment Numbers                 |   |
| DESCRIPTION OF CHANGE:                                  | The number of subjects to be enrolled in the observational cohort is changed to be capped at 440.   |
| RATIONALE:  | The current number of subjects in the observational cohort compared to the other cohort is higher than anticipated. The change is to cap the enrollment at the previously planned number. A higher number is not needed for the objectives of this cohort.  |
| 2. Changes in NephroCheck® (NC) Assessment       |   |
| DESCRIPTION OF CHANGE:                                  | The time window for post-surgical (coronary artery bypass graft and/or valve surgery) NC assessment is extended.  |
| RATIONALE:  | Review of the emerging data from the observation cohort showed a significant number of subjects had NC value > 0.3 after the current assessment window (i.e., 2 to 6 hours post-surgery). Based on available scientific literature and after confirmation with Key Opinion Leaders, NC increase within 24 hours after surgery is most likely due to an insult incited during surgery, and NC is approved to assess the acute kidney injury (AKI) risk in patients who have had acute cardiovascular compromise within the prior 24 hours. Extending the NC assessment window will identify subjects who have moderate or high risk for developing AKI, and therefore potentially be eligible for study treatment randomization. |
| 3. Addition of Details for Duration of Treatment |   |
| DESCRIPTION OF CHANGE:                                  | Parameters related to dosing of the investigational product are updated according to the extension of the NC assessment window.   |
| RATIONALE:  | The change is made to accommodate the extension of the NC assessment window. It is also expected that the wider treatment window after the surgery is supported to be effective based on preclinical data.  |

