## **4 SAMPLE SIZE**

Sample size of this study is 220 randomized subjects (110 subjects in the ASP1128 group and 110 subjects in the placebo group).

The above sample size provides 80% power to detect the difference between ASP1128 and placebo on the primary endpoint of AKI proportion in the case of not considering an interim analysis, assuming the followings:

- AKI proportion in the placebo group is 60%
- Relative risk of ASP1128 against placebo is 0.7 (30% reduction)
- 1-sided significance level is 0.05
- Drop-out rate is around 10%

In addition, an interim analysis at 60% of enrollment as described below is planned by East® 6 software. Considering the interim analysis, the power is 78%.

- Futility stop criteria: conditional power to detect the relative difference between ASP1128 and placebo on the primary endpoint of AKI proportion is less than 10%, that is, 1-sided p-value is larger than 0.259, when approximately 60% of the planned acute kidney injury based on serum creatinine within 72 hours after Time point 0 (T0) (AKI-SCr72h) data have been collected in the study.
- There will be no provision to stop the study for efficacy in the interim analysis, so no efficacy stop criteria are defined.

Approximately 1000 subjects will be screened to enroll 600 subjects who meet the presurgery selection criteria. It is expected that 1 out of 3 subjects enrolled will meet the postsurgery criterion of having a NC AKIRisk score  $> 0.3 \text{ (ng/mL)}^2/1000$  and can be randomized: the

number of subjects to be randomized is 220. The subjects that have an AKIRisk score of  $\leq 0.3$  at the postsurgery 2- to 6-hour assessment will be enrolled in the observational cohort.

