## **5.6 Prognostic Factor Analysis Set (PFAS)**

The Prognostic Factor Analysis Set (PFAS) consists of NC positive subjects, who are randomized to placebo group, and the NC negative subjects, who are in the observational cohort.

The PFAS will be used for exploring the prognostic factors and comparison with to NC test.

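### SAP 7.9.1 weights the prognostic set for the omitted ASP1128 arm but not for the 440 cap, so NephroCheck true positive and true negative rates are biased if that cap binds

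*SAP*

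**What the plan says.** The Prognostic Factor Analysis Set (PFAS) is built from two groups, "NC positive subjects, who are randomized to placebo group, and the NC negative subjects, who are in the observational" part of the study (SAP 5.6). SAP 7.9.1 states: "Population standardization is used in this analysis". It then says "Weighted Total (PFAS) is the set of NC negative group and NC positive group weighted by" a ratio. The numerator is "the number of subjects assigned to Placebo group + the number of subjects assigned to ASP1128 group" and the denominator is the number in the placebo group. NC-negative subjects receive no weight. In this set the SAP estimates unadjusted risk ratios, true positive rates (TPR) and true negative rates (TNR) for AKI-SCr72h, AKI-SCr7d, MAKE30 and MAKE90, for each factor in Table 13. Those factors include AKIRisk above 0.3 and above 0.7.

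SAP 4 gives the randomised size: "Sample size of this study is 220 randomized subjects (110 subjects in the ASP1128 group and 110 subjects in the placebo group"). Protocol 2.2.1 says: "The observational cohort will enroll a maximum of 440 subjects". The cap arrived with protocol version 2.0 (08 Oct 2020). Attachment 1 gives the reason: "The current number of subjects in the observational cohort compared to the other cohort is higher than anticipated". The same amendment extended the NC window from 2-6 hours to 2-22 hours after T0.

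SAP 4 does not mention the cap. It still describes 600 enrolled, 1 in 3 NC-positive and the 2- to 6-hour assessment. SAP versions 3.00 (July 2021) and 4.00 (January 2022) postdate the amendment. Their revision entries add observational-cohort analyses but list no change to the weight.

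**The concern.** TPR is the share of subjects with the event who carry the factor; TNR is the share without the event who do not. Both depend on how many NC-positives and NC-negatives are in the set. A weight meant to standardise to a population must therefore restore the mix of that population, which here is the enrolled, risk-factor-selected subjects who had NC tested.

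The SAP weight restores one departure from that mix, the missing ASP1128 arm. It does not restore the other: once 440 NC-negatives are in, further NC-negatives are not followed while NC-positives continue towards 220. From then on the mix is set by two enrolment limits. Evaluating NC and other characteristics for identifying subjects at risk is a stated exploratory objective, and these are the estimates that address it.

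**Working it through.** **Inputs.** Randomised: 220, 110 per arm (SAP 4). Cap on NC-negatives: 440 (Protocol 2.2.1, 7.1). AKI in untreated NC-positives: a = 60%, the placebo assumption in SAP 4. AKI in NC-negatives: b is not in the documents; assumed 5% to 20%. True NC-positive share over the study: π is not reported. The only stated value is the planned 1 in 3; 20%, 25% and 40% are assumed for comparison.

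**The plan's own figures.** With 110 × 0.9 = 99 per arm, 60% vs 42% and one-sided 0.05, power is 81.7% against the stated 80%, so the calculation that uses the 60% reproduces. The superseded enrolment text in Attachment 1 had 660 enrolled with 1 in 3 positive: 660/3 = 220 and 660 − 220 = 440. The cap is therefore the NC-negative count at a share of exactly 1/3. (SAP 4 now has 600, and 600/3 = 200, not 220.)

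**The mix.**
- Unweighted PFAS at both limits: 110/(110 + 440) = 20.0% NC-positive.
- SAP weight: (110 + 110)/110 = 2.
- Weighted PFAS at both limits: 220/(220 + 440) = 33.3%.

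**When the cap binds.** NC-negatives accrued by the time 220 are randomised = 220(1 − π)/π.
- π = 40%: 330. Cap not reached; the SAP weight gives 220:330 = 40%, which is correct.
- π = 1/3: 440. Cap just met; no error.
- π = 25%: 660, of whom 220 are not followed.
- π = 20%: 880, of whom 440 are not followed.

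**Rates for AKIRisk above 0.3.**

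TPR = πa / [πa + (1 − π)b]

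TNR = (1 − π)(1 − b) / [(1 − π)(1 − b) + π(1 − a)]

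| b (assumed) | SAP-weighted, 33.3%: TPR / TNR | True share 25%: TPR / TNR | True share 20%: TPR / TNR |
|---|---|---|---|
| 5% | 85.7 / 82.6 | 80.0 / 87.7 | 75.0 / 90.5 |
| 10% | 75.0 / 81.8 | 66.7 / 87.1 | 60.0 / 90.0 |
| 15% | 66.7 / 81.0 | 57.1 / 86.4 | 50.0 / 89.5 |
| 20% | 60.0 / 80.0 | 50.0 / 85.7 | 42.9 / 88.9 |

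Check by counts at b = 10%. SAP-weighted: 132 and 44 events, so TPR = 132/176 = 75.0% and TNR = 396/(396 + 88) = 81.8%. With all 880 NC-negatives: 132/(132 + 88) = 60.0% and 792/(792 + 88) = 90.0%.

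**Error.** The TPR excess runs from 85.7 − 80.0 = 5.7 points to 60.0 − 42.9 = 17.1. The TNR shortfall runs from 87.7 − 82.6 = 5.1 points to 88.9 − 80.0 = 8.9.

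**Dependence on a.** With a = 40% and b = 10%, TPR is 66.7 at the forced share against 57.1 (π = 25%) and 50.0 (π = 20%). TNR is 75.0 against 81.8 and 85.7. The errors are of similar size.

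**What is not affected.** The risk ratio for AKIRisk above 0.3 is a/b (0.60/0.10 = 6.0 at b = 10%) whatever π is, because it conditions on NC status. Estimates for the other Table 13 factors pool over NC-positives and NC-negatives, so they move with the mix.

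**The case against.** The strongest reply is that the error is conditional and that the amendment contains evidence against it. The remark about the larger observational cohort describes data under the 2-6 hour window. The same amendment widened the window because many subjects turned positive later, and Protocol 2.2.1 now allows up to four further tests until 22 hours. That moves subjects from negative to positive and raises the share. The only share in the documents is the planned 1 in 3, at which nothing goes wrong. A share of 25% means 220/0.25 = 880 NC-tested and 20% means 1,100, against about 600 enrolled and 1,000 screened in SAP 4. The analysis is also exploratory and has no bearing on the efficacy or safety conclusions.

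Most of this stands, and it is why the point is conditional. It does not remove the point, because the cap is a total over the whole study and an early excess of NC-negatives uses it up. As an assumed illustration, suppose 80 had been randomised at a 25% share by the time of the amendment. Then 240 NC-negatives are already in, leaving 140 positives and 200 negatives, and the share from then on would have to reach 140/340 = 41% for the cap not to bind. Whichever way it went, SAP 7.9.1 gives no rule for the case where the cap binds.

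**Conclusion.** The weight in SAP 7.9.1 does not deliver the standardisation it claims if 440 is reached before 220 are randomised. In that case TPR for AKIRisk above 0.3 is overstated by about 6 to 17 points and TNR understated by about 5 to 9. This assumes a true share of 20% to 25%, 60% AKI in NC-positives and 5% to 20% in NC-negatives. At a true share of 1/3 or more the error is zero. The amendment rationale makes a binding cap plausible; the documents report neither the actual share nor whether 440 was reached.

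Three stronger readings are not supported:
- A reader might infer that the rates are certainly wrong, or wrong by up to 25 points. The larger figure needs a share near 15%, or 220/0.15 ≈ 1,467 subjects tested, for which the documents give no support.
- A reader might infer that the other cap ("There will be a cap on the proportion of subjects randomized with a eGFR" below 45) also distorts the eGFR and CKD rows of Table 13. Nothing shows that it binds. SAP 7.4.1.1 plans for that stratum being under 10% of the FAS, and the documents do not say whether subjects beyond that cap would still have NC tested.
- A reader might take all cardiac surgery patients as the target. The target is the enrolled, risk-selected population.

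**What to change.** Add to SAP 7.9.1: if the observational cohort reaches 440 before randomisation ends, the main Table 13 TPR, TNR and pooled risk-factor estimates use only subjects operated on up to the date the cohort closed, with the placebo weight recomputed in that set. Show results by protocol version, because NC status was defined on 2-6 hours before version 2.0 and on 2-22 hours after it. Keep the full weighted PFAS as a secondary analysis. If the cap is not reached, the present weight stands.

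A weight of tested over followed for NC-negatives (660/440 = 1.5 at a 25% share, 880/440 = 2.0 at 20%) would keep all subjects. It should be used only if NC-negatives turned away after the cap can be identified in the eCRF. Protocol 8.2 lists the reason for failing among the screen-failure data but not the NC result.

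The cost is SAP wording and a date cut-off. Placebo subjects randomised after the cap leave the main analysis, so intervals widen, and the retained set leans towards the earlier NC window. SAP 4 should be brought into line with the protocol in the same revision (cap, NC window and the 600 figure).

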### **7.8.2 Analysis for Observational Cohort**

Potential risk factors (demographics, subject characteristics, biomarkers) for development of AKI and MAKE (listed below) will be explored:

- AKI-SCr72h
- AKI-SCr7d
- MAKE30
- MAKE90

Risk factor for AKI and MAKE will be compared to NC test in the PFAS. Details of the analysis method for PFAS will be described in the SAP.

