## **7 STATISTICAL METHODOLOGY**

### **7.1 General Considerations**

- For continuous variables, descriptive statistics will include the number of subjects (n), mean, standard deviation (SD), median, minimum and maximum. The number of digits to be used for the mean, standard deviation and median will be added one more digit to raw data with rounding off. The minimum and maximum will be presented with the same number of digit(s) as raw data. In addition, for pharmacokinetics (PK) variables, the coefficient of variation (CV) and the geometric mean will also be calculated.

Frequencies and percentages will be displayed for categorical data. Percentages by categories will be based on the number of subjects with no missing data, i.e. will add up to 100%. Frequencies and percentages will be rounded to one decimal place. For time-to-event variables, the number and percentage of subjects with the event using Kaplan-Meier method, the cumulative event rate will be estimated and a plot will be constructed.

- Summaries based on FAS and PPS (e.g. disposition, baseline and efficacy data) will be presented by planned randomization arm, unless specifically stated otherwise. Safety analysis and other summaries based on SAF will be presented by actual treatment received. Analysis of Observational Cohort based on PFAS will be presented by prognostic factor analysis arm.
- All statistical comparisons will be made using two sided tests at the  $\alpha=0.10$  significance level unless specifically stated otherwise. All null hypotheses will be of no treatment difference, all alternative hypotheses will be two-sided, unless specifically stated otherwise.
- All data processing, summarization, and analyses will be performed using SAS® Version 9.4 or higher on Red Hat Enterprise Linux. Specifications for Table, Figures, and Listings can be found in the TLF specifications for this study.
- For continuous variables that are recorded as “ $<X$ ”, “ $\leq X$ ”, “ $>X$ ”, or “ $\geq X$ ”, the value of “ $X$ ” will be used in the calculation of summary statistics if otherwise noted. The original values will be used for the listings.
- MedDRA will be used as the coding dictionary for adverse event and medical history.
- WHODrug Global B3 will be used as the coding dictionary for previous and concomitant medication.
- For the definition of subgroups of interest please refer to [Section [7.8](#)].

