#### **7.4.3 Subgroup Analysis**

[Analysis population: FAS, Analysis group: Randomization Arm]

- The estimate of the unadjusted risk ratio and 2-sided 90% confidence interval for the primary efficacy endpoint of AKI (AKI-SCr72h) proportion and secondary endpoints will be calculated by subgroups defined in [Section 7.8].
- In addition, the forest plot will be provided.
- For the continuous type subgroup factors, logistic regression model will be fitted for each continuous type subgroup factor 1 by 1. For each logistic regression model, response variable is primary or secondary endpoints (AKI-SCr72h, AKI-SCr7d, AKI-KDIGO72h, AKI-KDIGO7d, MAKE30 and MAKE90) and explanatory variables are treatment group, the subgroup factor and the interaction term of treatment group and the subgroup factor. The p-value of interaction will be calculated. The explanatory variables that will be used are listed as follows;
  - Left Ventricular Ejection Fraction (%),
  - AKIRisk Score ((ng/mL) $^2$ /1000) [Postsurgery],
  - Duration of CPB (hours),
  - Duration of Aortic Cross-Clamp (hours),
  - eGFR based on Serum Creatinine (mL/min/ $1.73\text{ m}^2$ ) [Baseline]

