**Table 13 Potential Risk Factors for Development of AKI and MAKE**

Risk Factor	Classification
Circulatory Shock	0: No 1: Yes
Nephrotoxic Drugs	0: No 1: Yes
Radiocontrast Agents	0: No 1: Yes
Poisonous Plants and Animals	0: No 1: Yes
Dehydration or Volume Depletion	0: No 1: Yes
Advanced Age ( $\geq 70$ years)	0: No 1: Yes
Female Gender	0: No 1: Yes
Black Race	0: No 1: Yes
CKD	0: No 1: Yes
Chronic Diseases (Heart, Lung, Liver)	0: No 1: Yes
Diabetes Mellitus	0: No 1: Yes
Anemia	0: No 1: Yes
Prior AKI	0: No 1: Yes
Left Ventricular Ejection Fraction ( $<40\%$ )	0: No 1: Yes
AKIRisk Score ( $>0.3 \text{ (ng/mL)}^2/1000$ ) [Postsurgery]	0: No 1: Yes
AKIRisk Score ( $>0.7 \text{ (ng/mL)}^2/1000$ ) [Postsurgery]	0: No 1: Yes
Peripheral Arterial Disease	0: No 1: Yes
Use of Intravenous Radio-contrast	0: No 1: Yes
Higher Risk Surgery	0: No 1: Yes
Duration of CPB ( $\geq \text{Median}$ )	0: No 1: Yes
Duration of Aortic Cross-Clamp 1 ( $\geq 0.5$ hours)	0: No 1: Yes
Duration of Aortic Cross-Clamp 2 ( $\geq 1.0$ hours)	0: No 1: Yes
eGFR Based on Serum Creatinine ( $<45 \text{ mL/min/1.73 m}^2$ ) [Baseline]	0: No 1: Yes

CKD: chronic kidney disease; AKI: acute kidney injury; CPB: cardiopulmonary bypass pump; eGFR: estimated glomerular filtration rate

In addition to the above, the following analyses will be conducted for Observational Cohort.

- Primary efficacy endpoint and secondary efficacy endpoints will be summarized for the subjects with NC positive within T0 + 24 hours and NC negative within T0 + 24 hours and all subjects in Observational Cohort. In the table, each stage of AKI-SCr72h and AKI-SCr7d and each individual outcomes of MAKE30/90 will also be summarized.
- For Observational Cohort, the association between MAKE30/MAKE90 (and also each individual outcomes, of all-cause mortality, initiation of RRT and eGFR based on SCr at day 30 (Visit 9)/day 90 (Visit 10) equal to or less than 75% of the baseline value) and primary, secondary and exploratory endpoint of AKI proportion is evaluated by a contingency table. The following endpoints of AKI proportion will be used;
  - AKI-SCr72h (primary endpoint) and each stage,
  - AKI-SCr7d (secondary endpoint) and each stage,
  - AKI-SCr stage 2 or 3 (within 72 hours after T0), and
  - AKI-SCr stage 2 or 3 (within 7 days after T0)

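### The prognostic-factor analysis reduces six continuous predictors to yes/no, so it has no discrimination measure that is comparable across factors for the promised comparison with NephroCheck

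*SAP*

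**What the plan says.** The second exploratory objective (Protocol 2.1.3, SAP 3.1.3) is to evaluate subject characteristics and biomarkers, including NC, for identifying subjects at risk of AKI. Protocol 7.8.2 turns this into a commitment: "Risk factor for AKI and MAKE will be compared to NC test in the PFAS". It leaves the method to the SAP.

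SAP 7.9.1 supplies the method. In the PFAS (placebo subjects, who are NC positive, plus the NC-negative observational cohort), placebo subjects are weighted by total randomized over placebo, about 2 under 1:1 allocation. For each factor in Table 13, the SAP lists these outputs: "The estimate of the unadjusted risk ratio, 2-sided 90% confidence interval, true positive rate, and true negative rate for AKI and MAKE".

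All 23 rows of Table 13 are No/Yes. Eight come from six variables measured on a continuous scale: age (70 years), ejection fraction (40%), AKIRisk (0.3 and 0.7), bypass time (sample median), cross-clamp time (0.5 h and 1.0 h) and baseline eGFR (45). No continuous model or c-statistic is given for the PFAS.

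The SAP does use continuous values elsewhere. Section 7.4.3 states: "For the continuous type subgroup factors, logistic regression model will be fitted for each continuous type subgroup factor 1 by 1". Five of the six variables (all but age) are listed there, but only to examine treatment interaction in the full analysis set.

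**The concern.** Section 7.9.1 is where the SAP has to deliver the comparison with NC, and its only accuracy measures are a true positive rate (TPR) and a true negative rate (TNR) at one cut. Such a pair reflects two things: how well the variable predicts, and how many subjects fall beyond the cut. Bypass time is cut so that half the subjects are positive. An eGFR below 45 is capped at 20% of randomized subjects (its share of the observational cohort is not stated). NC is positive at AKIRisk above 0.3. Setting these pairs side by side partly ranks the cuts rather than the predictors.

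At stake is the usefulness of an exploratory result: which characteristics or biomarkers, alone or against NC, are worth carrying forward to identify subjects at risk. No primary, secondary or safety conclusion depends on it.

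**Working it through.** **The plan's own figure.** The SAP states no power, effect size or event rate for the PFAS. Its only power figure, 80%, belongs to ASP1128 versus placebo: 60% against 60% × 0.7 = 42%, one-sided 0.05, and 110 × 0.9 = 99 evaluable per arm. With pooled variance under the null, z = [0.18√99 − 1.645√(2 × 0.51 × 0.49)] / √(0.60 × 0.40 + 0.42 × 0.58), which gives 81.7%. The figure reproduces, but it says nothing about the PFAS.

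**Cut-point dependence.** Assume controls N(0,1), cases N(0.262,1) and 30% cases. Discrimination is fixed at c = Φ(0.262/√2) = 0.573. For a cut q, TPR = 1 − Φ(q − 0.262) and TNR = Φ(q), with q chosen so that 0.3(1 − TPR) + 0.7·TNR equals the share below the cut.

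| Share beyond cut | TPR | TNR | Risk beyond / not beyond | Risk ratio | (TPR+TNR)/2 |
|---|---|---|---|---|---|
| 50% | 57% | 53% | 34.4% / 25.6% | 1.34 | 0.55 |
| 20% | 25% | 82% | 38.0% / 28.0% | 1.36 | 0.54 |
| 10% | 13% | 91% | 40.2% / 28.9% | 1.39 | 0.52 |

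The same predictor yields very different pairs. Averaging the pair does not recover 0.573 and still falls as the cut moves outward. The risk ratio is nearly stable, but it is not a measure of discrimination. A second set of inputs (odds ratio 1.5 per SD, AKI 28%) gives TPR/TNR of 61%/54%, 29%/83% and 16%/92% at the same three shares.

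**Information lost.** For a normal predictor with a linear effect, the efficiency of a cut relative to the continuous value is φ(q)²/[f(1 − f)], where f is the share beyond the cut. This is 0.64 at 50%, 0.49 at 20% and 0.34 at 10%.

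**Power, as illustration only.** Inputs from the documents: up to 440 NC-negative subjects (Protocol 7.1), 110 placebo subjects weighted 2, placebo AKI 60%, two-sided 0.10. Assumed: NC-negative AKI of 10% or 20%, a normal predictor with a log-linear effect, and the shares beyond the cut. The model is a weighted logistic regression with robust variance, with 1,500 simulated data sets per scenario. At an odds ratio of 1.3 per SD:

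| Predictor form | Power, NC-negative AKI 10% | Power, NC-negative AKI 20% |
|---|---|---|
| Continuous | 52% | 72% |
| Cut at median | 39% | 55% |
| 20% beyond cut | 36% | 50% |
| 10% beyond cut | 28% | 39% |

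Over odds ratios of 1.2 to 1.4 the loss is about 7 to 33 points. An unweighted simulation on a wider grid (N = 330 and 550, AKI 5% to 36%, odds ratios 1.2 to 1.5) gives about 1 to 36 points.

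The sign can reverse. If the true effect is a step at the cut (risk ratio 1.4, AKI 28%, N = 550), the yes/no form has more power than the continuous one: 79.6% against 63.0% at a median cut, and 67.7% against 45.3% with 20% beyond the cut.

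**The case against.** **No test is planned.** Section 7.9.1 explores and estimates. A reader might infer that power falls by 7 to 33 points, or that real predictors will be missed. The documents do not support either as fact: no PFAS hypothesis or power target exists, the inputs are assumed, 440 is a maximum, and a step effect reverses the result. What stands is a loss of information when effects are smooth.

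**The cuts are not arbitrary.** A reader might infer that only the 0.3 threshold has a basis. In fact eGFR 45 is the stratification factor and enrolment cap (Protocol 2.2.1 and 4.5), age 70 is in inclusion criterion 5, and ejection fraction 40%, median bypass time and AKIRisk 0.7 are subgroup cuts in Protocol 7.4.3. Only the two cross-clamp cuts appear in the SAP alone. Prespecification answers the charge of data-driven choice, but it does not make rates from different cuts comparable.

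**NC is itself a yes/no test, and the risk ratio is stable.** Both are true. Yes/no factors against NC at 0.3 is a fair question, and both halves of each TPR/TNR pair are shown. AKIRisk and cross-clamp time also get two cuts each. This covers the 15 rows that do not come from the six variables. It leaves the continuous ones without a cut-free measure.

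**A continuous AKIRisk result has its own problem.** Under Protocol 2.2.1 a negative NC may be repeated up to 22 hours and a positive leads to randomization. SAP Table 6, footnote 1, uses the last recorded score. The score therefore mixes sampling times under a rule that changed with protocol version 2.0. This stands and must be caveated.

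**Conclusion.** The point holds as a low-cost improvement to an exploratory analysis. Table 13 discards information on six continuous predictors, and section 7.9.1 offers no discrimination measure that is comparable across factors for the comparison promised in Protocol 7.8.2. The size is best shown by the TPR/TNR shift at fixed c = 0.573, from 57%/53% to 13%/91%, with the risk ratio nearly unchanged. That example assumes normal distributions with equal variance and 30% cases. The power figures are conditional on assumptions that the documents do not supply and are not bounds.

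**What to change.** In SAP 7.9.1, for age, ejection fraction, AKIRisk score, bypass time, cross-clamp time and baseline eGFR:

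- Add a PFAS-weighted logistic regression of each outcome (AKI-SCr72h, AKI-SCr7d, MAKE30, MAKE90) on the continuous value, with AKIRisk on the log scale. Report the odds ratio per SD and the weighted c-statistic with 90% CI.
- Compare these factors with NC on the c-statistic.
- Keep Table 13 in full as descriptive rows, including NC at 0.3 and every yes/no factor. Show c = (TPR + TNR)/2 for NC at 0.3, so that yes/no factors are set against NC in its yes/no form.
- Show the continuous AKIRisk result by protocol version, and state that the last recorded score mixes sampling times under the repeat-until-positive rule.

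The cost is SAP wording, one more table and some programming. The data are already collected, and logistic models on continuous values are already used in SAP 7.4.3. The downside is the AKIRisk caveat, which limits how far its c-statistic can be read.
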